### 3.3 Dose Limiting Toxicity (DLT) Definition

Severity of adverse events will be graded according to the National Cancer Institute Common Terminology Criteria for Adverse Events (NCI CTCAE) version 5.0. A DLT is defined as any death not clearly due to the underlying disease or extraneous causes or as any Grade ≥ 3 non-hematologic AE or any Grade ≥ 4 hematologic AE according to the NCI-CTCAE v 5.0, occurring during the DLT observation period that is related to any of the study interventions as determined by the Investigator or Sponsor at any dose and judged not to be related to the underlying disease or any previous or concomitant medication. A DLT must be confirmed by the SMC.

Any of the following adverse events occurring in the first 28 days of study participation are considered DLTs:

- 1. Grade 4 neutropenia ≥ 7 days or febrile neutropenia will be considered dose limiting.
- 2. Grade 3+ thrombocytopenia with bleeding or Grade 4 thrombocytopenia >7 days will be considered dose limiting.
- 3. A study intervention-related TEAE that in the opinion of the Safety Monitoring Committee (SMC) is of potential clinical significance such that further dose escalation would expose participants to unacceptable risk.
- 4. Delay by more than 4 weeks (28 days) in receiving the next scheduled cycle of study drug(s) due to persisting toxicities attributable to the study drug(s).
- 5. Non-hematologic toxicities:
  - a. Grade ≥ 3 nausea/vomiting or diarrhea lasting ≥ 72 hours while receiving optimal supportive medications,
  - b. Grade  $\geq$  3 fatigue lasting  $\geq$  7 days,
  - c. Grade3 pneumonitis of any duration,
  - d. Grade  $\geq$  3 rash lasting  $\geq$  7 days despite treatment,
  - e. Any Grade 4 immune related toxicities
  - f. Any other Grade ≥ 3 non-hematological toxicity (except for electrolyte abnormalities that are reversible and asymptomatic or hair loss which is not dose-limiting; as well as Grade 3 infusion-related reaction of any duration,
  - g. AST or ALT >3 × ULN and concurrent total bilirubin >2 × ULN of any duration without initial findings of cholestasis (elevated alkaline phosphatase, e.g., findings consistent with Hy's law or FDA definition of potential IP-induced liver injury).. For patients with hepatic metastases: AST, ALT >8X ULN; AST or ALT >5X ULN lasting ≥14 days.

The following treatment-related AEs are exceptions to the above mentioned DLT definition and are **not** considered to be DLTs:

- 1. Isolated Grade 4 lymphopenia without clinical correlate.
- 2. Any Grade 4 neutropenia < 7 days duration not associated with any clinical symptoms.
- 3. Other single laboratory values out of normal range that have no clinical correlate, and resolve to Grade ≤ 1 or to baseline within 7 days with adequate medical management.
- 4. Any Grade 3 autoimmune thyroid-related toxicity that clinical resolves to Grade ≤ 2 within 7 days of initiating therapy.
- 5. Grade 3 diarrhea persisting < 72 hours after initiation of medical management.
- 6. Grade 3 non-recurrent skin toxicity that resolves to Grade ≤ 1 in < 7 days after initiation of medical management.
- 7. Transient Grade 3 fatigue, local reactions, flu-like symptoms, fever, headache, nausea, and emesis that resolve to Grade ≤ 1 in < 48 hours after initiation of medical management.
- 8. Tumor flare phenomenon defined as local pain, irritation, or rash localized at sites of known or suspected tumor that resolve to Grade ≤ 2 within 6 days.
- 9. Grade 3 infusion-related reaction resolving within 6 hours from the end of infusion and controlled with medical management.

Elevation of amylase and/or lipase without clinical and/or radiographic evidence of pancreatitis are not considered DLTs, and the patient may resume treatment at any grade at the discretion of the treating physician in consultation with the PI.

During dose escalation, patients who receive <75% of the planned dose of the investigational products in the combination during Cycle 1 for reasons unrelated to study drug(s) are not evaluable for DLT and will be replaced.

In rare instances, an event may fall within the definition of a DLT as defined above but the event may not be considered a DLT (e.g. not clinically meaningful or significant). If this occurs, the PI will thoroughly review the event and supporting data, and the reasons for not considering the event a DLT will be clearly documented with supporting rationale. In addition, other events may occur that do not meet the definition of a DLT but are concerning to the PI, may then be considered to be DLTs.

In the event that a DLT is at least possibly related to the study drug(s), patients will halt treatment with the study drug(s) until symptoms resolve to the grade outlined in Section 5.2.5.2. Study drug(s) may be restarted as described in Section 5.2.5.

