- 9. Survival status: investigators will collect survival data for patients after progression of disease unless patient fully withdraws consent to consent to participate in the study. Approximately 1 year after the last dose of treatment, a chart review, patient visit, or telephone call will be conducted. The telephone call should be less than 5 minutes in duration, to obtain information regarding survival status.
- 10. Hematology: complete blood count (CBC), differential, and platelets.
- 11. Chemistry: sodium, potassium, chloride, bicarbonate, blood urea nitrogen (BUN), creatinine, glucose (non-fasting), calcium, phosphate, magnesium, alanine aminotransferase (ALT), aspartate aminotransferase (AST), alkaline phosphatase, bilirubin (total, direct, indirect), lactate dehydrogenase (LDH), total protein, albumin, uric acid, amylase, lipase, creatinine kinase, Adrenocorticotropic hormone (ACTH) and Testosterone (at screening only for CRPC patients), Gamma Glutamyl Transferase (GGT) and C-reactive Protein (CRP). No need to assess on Cycle 1 Day 1 if baseline assessment was performed within 2 days prior to that date. Chemistry labs will be performed on Days 1 and 15 of every cycle.
- 12. Thyroid Function: thyroid-stimulating hormone (TSH), free thyroxine (T4), and total triiodothyronine (T3) will be assessed at screening, Cycle 1 Day 1, and every 2 cycles or 8 weeks thereafter (C3D1, C5D1 etc.,) until disease progression or unacceptable toxicity, and also at the EOT visit.
- 13. Urine analysis will include color, appearance, specific gravity, pH, protein, glucose, ketones, blood, bilirubin, and microscopy including WBC/high power field (HPF), and RBC/HPF, if clinically indicated. Dipstick is acceptable. Urine analysis will be at screening and Day 1 of every cycle. No need to repeat on Cycle 1 Day 1 if baseline assessment was performed within 2 days prior to that date.

- 14. Coagulation test includes prothrombin time (PT), international normalization ratio (INR), and activated partial thromboplastin time (aPTT). Coagulation tests will be performed at screening, and Day 1 of every cycle. No need to repeat on Cycle 1 Day 1 if baseline assessment was performed within 2 days prior to that date.
- 15. Avelumab will be administered to patients at 800 mg, IV every 2 weeks, starting on Cycle 1 Day 1 (Days 1 and 15 of every cycle).

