- 16. M6620 may be administered to patients in the dose escalation phase at 1 of 3 doses: 240 mg/m² (dose level 1), 480 mg/m² (dose level 2), or 120 mg/m² (dose level -1) IV weekly, starting on Cycle 1 Day 1 (Days 1, 8, 15, and 22 of every cycle). M6620 will be administered to patients in the dose expansion phase of at the recommended phase 2 dose (RP2D) established in the dose escalation phase.
- 17. When M6620 and Avelumab are to be administered on the same day (e.g. C1D1, C1D15), avelumab will be infused first, with an interval of at least 1 hour before infusion of M6620.
- 18. CT, MRI, or PET-CT scans will be performed at screening, and then every 2 cycles or 8 weeks (± 7 days) for the first year of treatment. Thereafter, tumor assessments will be performed every 3 cycles or 12 weeks (± 7 days) independent of cycle delays. Confirmatory scans will also be obtained ≥ 4 weeks following initial documentation of objective response (OR) or progression of disease (PD). The type of scan obtained is at the discretion of the investigator as appropriate for the disease. However, the same method should be used for the duration of the study. Baseline brain CT or MRI scan is required for all high risk patients (such as breast, melanoma and other cancer types as determined by the PI/sub I) at baseline (screening). Patients with stable brain metastases present at baseline (screening) will have brain CT or MRI scans performed at each tumor assessment. If bone metastases are present at baseline (screening), then repeat bone imaging is required every 8 weeks for the first 52 weeks of study treatment and every 24 weeks thereafter. Bone imaging is required at the time of confirmation of CR for patients who have bone metastases.
- 19. Relevant tumor markers (e.g., CA125, PSA, and CEA) will be assessed at screening, and on Day 1 of every cycle (± 7 days) this will include blood draws at EOT and Long Term Follow-up.
- 20. One tumor biopsy is mandatory (C1D15), although not mandatory all other tumor biopsies will be strongly encouraged. A core tissue biopsy may be required at baseline if no leftover tissue is available for screening, tissue is older than 1 year, or there is not enough tissue for testing. Tumor biopsies may be performed at baseline (pre-treatment), Cycle 1 Day 15, and at the time of progression/EOT (where feasible).

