# 3.4 Maximum Tolerated Dose (MTD) Definition

In the dose escalation phase for the combination of M6620 and avelumab, patients will be assigned sequentially in groups of up to 6 patients at each dose level. Three to 6 patients will initially be enrolled at each dose level for DLT observation. A total of 6 patients will be enrolled at each dose level in the event that a DLT is observed in 1 of the first 3 patients and/or additional safety data are needed.

The MTD is defined as the highest dose level with less than 2 patients with DLT out of at least 6 patients at the dose level. Management and dose modifications associated with adverse events are outlined in subsequent protocol sections.

The DLT assessment window is 28 days (1 cycle). In the absence of DLTs, patients may continue consecutive treatment. For patients who experience a DLT, they may continue treatment with modifications if the toxicity resolves and at the discretion of the treating physician and the Pl. In the absence of clinical deterioration and if the investigator believes that the patient continues to receive benefit from the treatment, patients may continue to receive study drug(s) after the first indication of progressive disease until a confirmatory scan is obtained.

To understand and safeguard against potential cumulative toxicities the study team will continue to monitor the occurrence of study drug related SAEs and AEs throughout the treatment period and during potential treatment extensions to allow for dose correction in the event of cumulative immune-mediated toxicities.

[figure not shown]
Delayed onset of significant toxicities will be evaluated on a case-by-case basis at the discretion of the PI in consultation with the Safety Monitoring Committee (SMC). At minimum, a review and discussion of potential delayed onset of significant toxicity will take place at review prior to a dose escalation decision.

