### 3.5 Dose Escalation and Stopping Rules

The decision to proceed to the next dose level will be made after the first 3 patients in a dose level have completed 28 days (1 cycle) of dosing. Prior to advancing/changing dose levels, a dose

level summary will be completed and submitted to SMC for review and approval. The data discussed at the SMC during escalation/expansion phases and the minutes of the meetings will be submitted to the IND Office Medical Affairs & Safety group.

Figure 4: Dose Escalation Rules:

Dose escalation will occur at the planned dose levels until the MTD is determined. The MTD is defined as the highest dose level with less than two patients with DLT out of at least six patients. The recommended phase 2 dose (RP2D) will be based on the safety and preliminary efficacy data from the dose escalation and dose expansion arms. Intra-patient dose escalation will only be allowed if the patient experienced grade ≤1 AEs at the current dose.

All enrolled participants will be considered in the DLT analysis. If any patient should be excluded from the analysis, the reason(s) should be clearly documented (see Section 3.3). If a DLT occurs at a dose level with 3 patients within the first 28 days, 3 additional patients will be enrolled at that dose level. If at any time, at least one third of the participants at a dose level (33%) experience DLTs, the MTD will be reassessed and the next lowest dose level will be considered the MTD.

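### On nominal days the 28-day DLT window holds one scheduled post-dose blood count (C1D15), so a silent Grade 4 cytopenia long enough to be a DLT can go unsampled

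*Combined protocol and SAP*

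**What the plan says.** Section 3.3 has two hematologic DLT criteria with a duration limit: "Grade 4 neutropenia ≥ 7 days or febrile neutropenia will be considered dose limiting" and "Grade 3+ thrombocytopenia with bleeding or Grade 4 thrombocytopenia >7 days will be considered dose limiting". The exceptions in the same section remove "Any Grade 4 neutropenia < 7 days duration not associated with any clinical symptoms", so for an asymptomatic patient duration decides the classification. Section 3.4 fixes the observation period: "The DLT assessment window is 28 days (1 cycle").

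The hematology row of the Study Calendar is marked at screening, C1D1, C1D15 and C2D1, and is blank at C1 Days 2-4, 8, 16-18 and 22. Footnote 10 gives content only: "Hematology: complete blood count (CBC), differential, and platelets". The chemistry row has the same Cycle 1 pattern, and its footnote confirms it: "Chemistry labs will be performed on Days 1 and 15 of every cycle". Footnote 16 sets M6620 at "IV weekly, starting on Cycle 1 Day 1 (Days 1, 8, 15, and 22 of every cycle"). The extra blood draws on Days 2-4 and 16-18 are M6620 PK samples (footnote 23).

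Section 7.1.4 requires hematology and a short chemistry list to be reviewed before dosing, with a reference to the Study Calendar.

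**The concern.** The two criteria ask whether a Grade 4 value lasted about a week, but the schedule looks at the blood once after dosing within four weeks. C1D1 labs precede the first dose (Section 6 puts safety labs before drug), and C2D1 is nominally one day past the window. A patient could meet a DLT criterion between draws without anyone knowing, and could receive the Day 8 or Day 22 infusion during the episode.

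DLT incidence is a primary endpoint (2.2.1). The escalation decision follows the first 3 patients completing 28 days (3.5), the next step doubles M6620 from 240 to 480 mg/m², and the MTD requires fewer than 2 patients with DLT among at least 6. At these cohort sizes one unobserved event could change a decision.

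**Working it through.** The plan states no figure on this point, so there is none to reproduce.

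**Inputs.** Post-dose draws on nominal Days 15 and 29 (Study Calendar); observation on Days 2-28 (3.4); qualifying length L ≥ 7 days for neutrophils and L ≥ 8 whole days for platelets (3.3). Uniform onset is my assumption.

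**Gaps.** Days 2-14 and Days 16-28 have no scheduled count: 13 days each.

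**Formula.** An episode of L days is missed if it lies wholly inside a gap. A gap of g days contains g − L + 1 such onsets (zero if negative), so two 13-day gaps give 2 × (14 − L). The denominator is 28 − L onsets if the episode must end by Day 28, or 27 onsets if every start on Days 2-28 counts. The second base adds only late episodes still present at the Day 29 count, so the numerator does not change.

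| L (days) | Missed onsets | Ends by Day 28 | All onsets, Days 2-28 |
|---|---|---|---|
| 7 | 14 | 14/21 (67%) | 14/27 (52%) |
| 8 | 12 | 12/20 (60%) | 12/27 (44%) |
| 10 | 8 | 8/18 (44%) | 8/27 (30%) |
| 13 | 2 | 2/15 (13%) | 2/27 (7%) |
| 14 | 0 | 0/14 | 0/27 |

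**Visit windows.** C1D15 and C2D1 may each move by 2 days, so C2D1 can fall on Day 27 or 28, inside the DLT window. Over the 25 combinations the first gap is 11-15 days and the second 9-17 days, and the longer of the two is never below 12. For seven-day episodes ending by Day 28, 12 to 14 of 21 onsets are missed in every combination. The windows do not close the gap.

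**After adding C1D8 and C1D22.** Nominal gaps fall to 6 days (6 − 7 + 1 = 0), so 0 of 21 seven-day onsets are missed. If visits drift to unfavorable ends of their windows, some return. With C1D8 on Day 6 and C1D15 on Day 17, Days 7-16 are empty (10 − 7 + 1 = 4). With C1D22 on Day 20 and C2D1 on Day 29 or later, Days 21-28 are empty (8 − 7 + 1 = 2). The worst case is thus 6 of 21.

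**The case against.** The best counterargument is Section 7.1.4. Its calendar reference may attach to drug administration, and M6620 is administered on Days 8 and 22. On that reading a count is already required before all four Cycle 1 doses; footnote 10, unlike the chemistry footnote, limits hematology to no particular days. This stands as a real ambiguity. It does not remove the point, because the hematology row is blank at those visits while the vital-signs row is marked at both. A site following the row would draw nothing. On either reading the text needs correcting.

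Second, other safeguards exist. Febrile neutropenia and bleeding present clinically. AEs are recorded at each visit (footnote 8), and 7.1.5 calls for abbreviated examinations with attention to skin and mucosa. A Grade 4 value, once found, is followed under 5.2.5.2 and 8.6.1. Section 3.5 adds: "If at any time, at least one third of the participants at a dose level (33%) experience DLTs, the MTD will be reassessed". SMC review and the expansion toxicity rule in 9.6 come on top. These limit the exposure to silent episodes that resolve between draws, but the follow-up and stopping rules act on known events and cannot recover an unmeasured nadir.

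Third, uniform onset has no support in the documents: it makes Grade 4 on the day after the first dose as likely as on any other day. That is fair. The fractions describe the schedule, not the drug.

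**Conclusion.** The point holds as a limited gap in sampling, and it is worth closing because closing it is cheap. On nominal days a plan followed as its calendar row reads can miss asymptomatic Grade 4 neutropenia of 7-13 days or Grade 4 thrombocytopenia of 8-13 days, and can dose on Days 8 and 22 without a count. For a seven-day episode the illustrative share of missed onsets is 52% or 67%, depending on the denominator.

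A reader might infer that about two thirds of hematologic DLTs will be missed, or that the MTD will be set too high. The documents support neither. The 67% applies only to seven-day silent episodes ending by Day 28 with uniform onset, and without a Grade 4 rate or nadir timing the effect on MTD selection is unknown. Nor do the documents show that the sponsor intended dosing without a count; 7.1.4 leaves that open.

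**What to change.** Mark hematology (CBC with differential and platelets) at C1D8 and C1D22 in the Study Calendar, and state the days in footnote 10. In 7.1.4, state that a count is reviewed before every Cycle 1 M6620 infusion.

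Ask that Cycle 1 counts be kept about 7 days apart where feasible. A hard cap is not needed: only 15 of the 625 possible window combinations have every interval at 7 days or less, so a strict rule would force separate draws. Repeat counts after a Grade 4 value can follow the existing rules in 5.2.5.2 and 8.6.1, with a note that the interval must be short enough to establish the 7-day duration.

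Scoring an unresolved Grade 4 count as a DLT by default is optional. It changes the DLT definition and does not recover nadirs that were never sampled.

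The cost is two extra blood counts per patient at infusion visits that already take place, and a short amendment.

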#### **5. STUDY TREATMENTS**

The trial regimen will be administered in 28-day cycles. The investigational products to be administered in this trial are: M6620 and avelumab. For both dose escalation and expansion, treatment will continue until disease progression, unacceptable toxicity, and/or withdrawal of patient consent.

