#### 5.2.5.2 Dose Delays

Patients experiencing Grade 3 or 4 potentially treatment related toxicity or intolerable Grade 2 toxicity despite supportive care should have their treatment interrupted/delayed. Appropriate follow-up assessments should be done until adequate recovery (or until deemed irreversible) occurs as assessed by the Investigator. A treatment delay of more than 4 weeks due to lack of recovery will result in discontinuation of the patient from the treatment, unless continuation (with dose reduction) upon subsequent recovery is considered in the patient's best interest by the investigator (e.g. proven clinical benefit).

A new cycle of treatment may begin only if:

- a. ANC ≥ 1000/µL
- b. Platelet count ≥ 100,000/µL
- c. Hemoglobin ≥ 8.5 g/dL
- d. Non-hematologic toxicities have returned to baseline or Grade ≤ 1 severity (or, at the investigator discretion, Grade ≤ 2 if not considered a safety risk for the patient).

Withhold scheduled dose for liver function test related AEs (including asymptomatic) Grade  $\geq 3$  until return to baseline or Grade  $\leq 1$  severity. In cases of potential liver injury, consultation with a hepatologist should be considered in the decision to initiate treatment with anti-inflammatory medications.

If these conditions are not met, treatment must be delayed by 1 week. If, after a 1-week delay, all toxicities have recovered within the limits described above, treatment with study drugs, can be resumed. Both study drugs should be delayed simultaneously if applicable. If the patient has not recovered after 1 week of delay, treatment may be delayed by 1 more week. However, initiation of the next cycle can only be delayed by a maximum of 4 weeks (28 days). Therefore, if persisting toxicity does not allow for the resumption of treatment, the patient will be permanently discontinued.

For all ≥ Grade 3 hematological or non-hematological AEs that are NOT study drug-related, after consultation with the Medical Monitor and at the discretion of the treating physician, study drug dosing may be continued.

Elevation of amylase and/or lipase without clinical and/or radiographic evidence of pancreatitis are not considered DLT, and the patient can resume treatment at any grade at the discretion of the treating physician in consultation with the PI.

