# 9.1.2 DLT Analysis Set

The DLT analysis set is a subset of the safety analysis set and includes all enrolled patients in the dose escalation phase, receive at least one dose of the combination treatment, and either experience DLT during the first cycle (28 days) of treatment, or complete the DLT observation period for the first cycle of treatment.

Patients without DLTs who withdraw from study treatment before receiving at least 75% of the planned dose of each of the investigational products in the combination in Cycle 1 for reasons other than toxicity, which are attributable to the investigational products are not evaluable for DLT. Additional patients will be enrolled in the specific cohort to replace patients who are not considered DLT evaluable.

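### The DLT criterion for a cycle delay of more than 28 days cannot be met until about Day 58, a month after the 28-day DLT window and the earliest escalation decision

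*Combined protocol and SAP*

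**What the plan says.** Item 4 of the DLT list in section 3.3 is a dosing delay attributed to persisting drug toxicity: "Delay by more than 4 weeks (28 days) in receiving the next scheduled cycle of study drug(s". The sentence that introduces the list sets its time limit: "Any of the following adverse events occurring in the first 28 days of study participation are considered DLTs".

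Four other places fix the timing:

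- Section 5: "The trial regimen will be administered in 28-day cycles".
- Section 3.4: "The DLT assessment window is 28 days (1 cycle".
- Section 3.5: "The decision to proceed to the next dose level will be made after the first 3 patients in a dose level have completed 28 days", which the section equates with one cycle.
- Section 9.1.2: a patient enters the DLT analysis set by having a DLT in the first 28-day cycle, or if they "complete the DLT observation period for the first cycle of treatment".

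Section 5.2.5.2 applies the same limit to treatment: "initiation of the next cycle can only be delayed by a maximum of 4 weeks (28 days". Beyond it the patient normally stops for good, with case-by-case exceptions.

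**The concern.** The plan means a toxicity delay of more than 28 days to be a DLT by rule. On the plan's own calendar, that rule cannot operate before the cohort is judged. Item 4 matters for patients whose Cycle 2 is held for a toxicity that meets no other DLT item. These are mainly patients with cytopenia below Grade 4 that still fails the restart limits in 5.2.5.2 (ANC 1000/µL, platelets 100,000/µL, hemoglobin 8.5 g/dL). Some will have Grade 2 non-hematologic toxicity that the investigator judges a safety risk.

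Such a patient can be on the way to permanent discontinuation for drug toxicity and still count as free of DLT when the one planned upward step is decided. That step doubles M6620 from 240 to 480 mg/m². With three to six patients per level, one patient can change the decision: 0 of 3 against 1 of 3 determines whether three more are enrolled, and 1 of 6 against 2 of 6 determines the MTD.

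**Working it through.** **Day count (Day 1 = Cycle 1 Day 1)**

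| Step | Source | Result |
|---|---|---|
| Last day of the DLT window | 3.4 | Day 28 |
| Cycle 2 Day 1 due | 5 (28-day cycles) | 1 + 28 = Day 29 |
| Delay equals 28 days | 3.3 item 4 | 29 + 28 = Day 57 |
| Delay first exceeds 28 days | 3.3 item 4 | 29 + 29 = Day 58 |
| Same, with the ±2-day visit window | Study Calendar | Day 56 to Day 60 |

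Item 4 is therefore first met 58 − 28 = 30 days (28 to 32) after the window closes. A hold within Cycle 1 does not change this, because section 5.2.5.1 says that omitted doses are not made up within the cycle.

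**Possible effect on the dose decision**

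The plan states no figure to reproduce, and the documents give no toxicity rates, so every risk below is an assumption. Let q be a patient's probability of a counted DLT. Suppose that a level clears on 0 of 3, or on 1 of 3 followed by 0 of 3 more:

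P(clear) = (1 − q)³ + 3q(1 − q)² × (1 − q)³

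The MTD rule requires fewer than 2 of 6 patients with a DLT:

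P(<2 of 6) = (1 − q)⁶ + 6q(1 − q)⁵

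For q = 0.10, P(clear) = 0.729 + 0.243 × 0.729 = 0.906.

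| In-window risk + delay-only DLTs counted | q | P(clear) | P(<2 of 6) |
|---|---|---|---|
| 10% + 0 (delays missed) | 0.10 | 0.906 | 0.886 |
| 10% + 1 point | 0.11 | 0.889 | 0.866 |
| 10% + 2 points | 0.12 | 0.871 | 0.844 |
| 10% + 5 points | 0.15 | 0.814 | 0.776 |
| 10% + 10 points | 0.20 | 0.709 | 0.655 |

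With an assumed in-window risk of 20%, P(clear) is 0.709 when delays are missed. It is 0.600, 0.494 or 0.396 when a further 5, 10 or 15 points are counted.

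For any given pair of rates, the gap between the first row and a later row is an upper bound on the effect. It assumes that committee and investigator review catches none of these patients.

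**The case against.** The strongest counter-argument is that item 4 should not be read so literally. A delay is a consequence of an adverse event. The natural meaning is that the toxicity starts in Cycle 1 and its persistence is judged later, as with other items that carry a duration. That is a fair account of the intent. It does not settle the timing: on that reading, item 4 status is still unknown until about Day 58.

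The plan also has required steps before escalation. The SMC must approve a dose-level summary (3.5), and potential delayed toxicity must be discussed (3.4). The SMC can call an event a DLT under item 3, the principal investigator can reclassify events, and a cohort can be expanded when more safety data are needed. Day 28 is the earliest decision time, not a deadline, and the hold is visible by Day 29. All of this lowers the risk. However, the outcomes of these steps are discretionary, and none of them says whether the patient on hold is counted, pending or not evaluable. The reassessment at one third in 3.5 can act on item 4 only once the delay is established, which may be after escalation.

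Three limits stand:

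- **The group is small.** Grade 2 non-hematologic toxicity may restart at the investigator's discretion. Section 5.4.3 also allows growth factors for treatment-emergent neutropenia.
- **The MTD column is likely to overstate the effect.** If the second three patients enrol after the first three finish Day 28, the first three are at about Day 56 or later when six are judged. Their holds would be nearly resolved.
- **Figure 4 (Dose Escalation Rules) could not be read in the copy reviewed.** If it contains a waiting rule, the escalation part of the concern falls away.

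**Conclusion.** The concern holds. As written, item 4 cannot be met inside the window that governs it, and no readable text makes escalation wait for a patient held at Day 29. The day count rests only on the protocol's own cycle length and visit window.

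The size of the effect is unknown. Under the assumed 10% in-window risk, 1 to 2 points of delay-only DLTs change the clearance probability by 0.02 to 0.04. A change as large as 0.20 needs one patient in ten to have a delay of more than 28 days and no other DLT, and nothing in the documents supports a rate that high. The case for changing the text does not depend on those figures. A stated DLT criterion is left to judgement at the one upward dose step and at the MTD call, and it can be repaired cheaply.

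**What to change.** - **Section 3.3, item 4:** state that the delay is a DLT when the toxicity causing it began in Cycle 1, even though the delay passes 28 days only after the window has closed.
- **Sections 3.5 and 9.1.2:** state that a patient whose Cycle 2 is on hold for drug-related toxicity at Day 29 is pending. The patient is not counted as free of DLT for escalation or for the MTD until Cycle 2 starts or the 28-day limit is exceeded.
- **Figure 4:** check that it agrees with both changes.

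The cost is two or three sentences of protocol wording. An escalation decision may wait about four weeks, from Day 29 to Day 58 at the latest on nominal dates, and only when a patient is on such a hold.

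### Sections 3.3 and 9.1.2 give conflicting DLT-evaluable rules: one can drop a patient who had a DLT, the other can count an under-dosed patient as DLT-free

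*Combined protocol and SAP*

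**What the plan says.** Three sections of the combined protocol and SAP bear on who counts in the escalation decision.

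- **Section 3.3.** An escalation patient who receives less than 75% of the planned dose of the combination "during Cycle 1 for reasons unrelated to study drug(s) are not evaluable for DLT and will be replaced". The rule neither exempts a patient who has already had a DLT nor requires withdrawal from treatment.
- **Section 9.1.2.** The DLT analysis set holds treated escalation patients who "either experience DLT during the first cycle (28 days) of treatment, or complete the DLT observation period for the first cycle of treatment". That sentence sets no minimum dose. The exclusion that follows covers "Patients without DLTs who withdraw from study treatment before receiving at least 75% of the planned dose of each of the investigational products", for reasons other than toxicity. These patients are replaced.
- **Section 3.5.** "All enrolled participants will be considered in the DLT analysis". The next sentence reads "If any patient should be excluded from the analysis, the reason(s) should be clearly documented" and refers the reader to Section 3.3.

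Sections 3.4 and 3.5 define the MTD as the highest level with fewer than 2 patients with a DLT among at least 6. Footnotes 15 and 16 of the Study Calendar give the Cycle 1 doses: avelumab on Days 1 and 15, and M6620 on Days 1, 8, 15 and 22.

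**The concern.** The two detailed rules differ in three ways: whether a patient with a DLT can be replaced, whether an under-dosed patient must withdraw to be excluded, and whether 75% applies to each drug. Nothing says which section prevails.

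With three to six patients per level, one reclassified patient can change the decision. Discarding a patient with a DLT, or adding a DLT-free patient who did not receive the level, makes a too-toxic level easier to pass. The MTD and RP2D are a primary objective, and the RP2D is the dose given in expansion.

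**Working it through.** **Step 1. Classify patient profiles under the two rules.**

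| Profile | Section 3.3 | Section 9.1.2 |
|---|---|---|
| (a) DLT, then falls below 75% for a reason unrelated to study drug | Replaced | Counted, as a DLT |
| (b) No DLT; misses Day 15 (both drugs) and Day 22 (M6620) for an unrelated reason; does not withdraw; reaches Day 28 | Replaced | Counted, as DLT-free |
| (c) No DLT; misses only the Day 15 avelumab for an unrelated reason; does not withdraw | Depends on how 75% is read | Counted, as DLT-free |

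Dose fractions:
- Profile (b): M6620 2/4 = 50% and avelumab 1/2 = 50%. The patient is below 75% on any reading of 3.3. Section 5.2.5.1 foresees interruptions for reasons other than toxicity, such as elective surgery, so the profile is not contrived.
- Profile (c): avelumab 1/2 = 50%, but (4 + 1)/(4 + 2) = 5/6 = 83% of all infusions. The patient is below the line if 75% applies to each product and above it if infusions are pooled. Section 9.1.2 says *each*; Section 3.3 does not.

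**Step 2. Effect of one patient.** 2/6 = 33% fails the MTD rule and also meets the one-third criterion in 3.5. 1/6 = 17% passes. Replacing one of two DLT patients with a DLT-free patient reverses the decision.

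**Step 3. Pass probability.** The plan states no operating characteristic for escalation, so there is no figure of its own to reproduce. Take six counted patients with true DLT rate p, treated as a fixed set and not as the full cohort sequence:

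P(pass) = (1 − p)^6 + 6p(1 − p)^5

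At p = 0.4: 0.0467 + 0.1866 = 0.233.

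*A share r of DLT patients is replaced.* The DLT rate among counted patients becomes p(1 − r)/(1 − pr).
- r = 5%: 0.38/0.98 = 0.388, so P(pass) = 25.3%.
- r = 10%: 0.36/0.96 = 0.375, so P(pass) = 27.4%.

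*One of six counted patients is under-dosed, with DLT risk f × p.* The other five have P(0 DLTs) = 0.6^5 = 0.0778 and P(1 DLT) = 5 × 0.4 × 0.6^4 = 0.2592.
- f = 0.5 (risk 0.2): 0.0778 + 0.2592 × 0.8 = 28.5%.
- f = 0: 0.0778 + 0.2592 = 33.7%.

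| True DLT rate | All DLTs counted, none under-dosed | 5% of DLT patients replaced | 10% replaced | 1 of 6 under-dosed, half risk | 1 of 6 under-dosed, no risk |
|---|---|---|---|---|---|
| 20% | 65.5% | 67.5% | 69.5% | 69.6% | 73.7% |
| 30% | 42.0% | 44.3% | 46.8% | 47.4% | 52.8% |
| 40% | 23.3% | 25.3% | 27.4% | 28.5% | 33.7% |
| 50% | 10.9% | 12.2% | 13.6% | 14.8% | 18.7% |

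The values of p, r and f are assumptions, because the documents give no rate of under-dosing or replacement. The direction is the same in every row.

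**The case against.** **There are not three populations.** A reader might infer a third from the opening words of 3.5. Read whole, 3.5 allows documented exclusions and points to 3.3, so two rules conflict. This stands. The wording of 3.5 still needs tidying.

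**Profile (a) is narrow.** Section 3.3 replaces only for unrelated reasons, and it halts study drug after a DLT that is at least possibly related. Doses missed after a DLT will therefore usually be drug-related, and the patient stays evaluable. Disease progression is an unlikely cause within 28 days, since the first scheduled scan is at 8 weeks. This largely stands, but Section 3.4 lets DLT patients continue treatment, so an unrelated miss remains possible.

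**Replacement need not lead straight to escalation.** A reader might infer that one DLT in three, once replaced, becomes a clean cohort. Sections 3.4 and 3.5 call for three more patients when a DLT is observed or occurs, with no mention of evaluability. That inference fails. What remains is the count among six.

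**Drug-related under-dosing.** Section 5.2.5.2 states: "Patients experiencing Grade 3 or 4 potentially treatment related toxicity or intolerable Grade 2 toxicity despite supportive care should have their treatment interrupted/delayed". A reader might infer that a level few patients can receive could still qualify as the MTD, because a patient under-dosed by drug-related toxicity short of a DLT stays evaluable and can count as DLT-free. Both sections treat this patient alike, so it is not a contradiction. The Safety Monitoring Committee (SMC) and the PI may also class other events as DLTs (3.3), and the SMC approves each change of level (3.5). Whether such patients should count as DLTs is a clinical rule, and none is proposed here.

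**Expansion has its own toxicity monitoring.** Section 9.6 stops at 5/10 or 8/20 DLTs. Table 7 gives an early-stopping probability of 0.63 at a true rate of 40% (0.623 on recomputation). This is a real later safeguard, but it acts only after patients have been treated at the selected dose.

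**Conclusion.** The conflict between 3.3 and 9.1.2 is in the text and does not depend on any assumed rate. As written, 3.3 can replace a patient with a DLT, and 9.1.2 can count as DLT-free a patient who received half of each drug. Whether one missed avelumab dose makes a patient non-evaluable under 3.3 cannot be settled from its wording.

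The size is modest. At an assumed DLT rate of 40%, the probability of passing rises by about 2 to 4 percentage points if 5–10% of DLT patients are replaced (25.3 − 23.3 = 2.0; 27.4 − 23.3 = 4.1). It rises by about 5 to 10 points if one of six counted patients is under-dosed (28.5 − 23.3 = 5.2; 33.7 − 23.3 = 10.4). Both shifts favour a higher MTD. The documents do not support a claim of three separate populations, or that a replaced DLT leads directly to escalation. The point should be corrected because the MTD is a primary objective, one patient can decide it, and the remedy is wording.

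**What to change.** Reconcile the passages into one DLT-evaluable set, stated once and used in 3.3, 3.5 and 9.1.2:

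1. Count every escalation patient with a DLT, whatever dose was received. Section 9.1.2 already does this; add the exemption to 3.3.
2. Replace only DLT-free patients who fall below 75% of the planned Cycle 1 dose for reasons unrelated to study drug, whether or not they withdraw. Section 3.3 already needs no withdrawal; remove that condition from 9.1.2.
3. State in both sections whether 75% applies to each product or to the combination pooled.
4. In 3.5, restrict the statement about all enrolled participants to this set.

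The cost is wording in three sections and an occasional extra replacement patient. The DLT criteria themselves do not change.
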